## **7.7. Changes From Protocol-Specified Safety Analyses**

There are no deviations from the protocol-specified safety analyses.

## 8. PHARMACOKINETIC ANALYSES

Concentrations of filgotinib and GS-829845 in plasma will be determined using validated bioanalytical assays. Plasma concentrations of filgotinib and the active metabolite of filgotinib, GS-829845, will be listed and summarized using descriptive statistics (eg, sample size, arithmetic mean, geometric mean, % coefficient of variation, standard deviation, median, minimum and maximum).

### 8.1. PK Analyses Related to Intensive PK Sampling

CCI

#### 8.1.1. Estimation of Pharmacokinetic Parameters

PK parameters will be estimated using Phoenix WinNonlin® software using standard noncompartmental methods. The linear/log trapezoidal rule will be used in conjunction with the appropriate noncompartmental model, with input values for dose level, dosing time, plasma concentration, and corresponding real-time values, based on drug dosing times whenever possible.

All predose sample times before time-zero will be converted to 0. Predose samples may also serve as the 24-hr post dose sample if appropriate.

For area under the curve (AUC), samples BLQ of the bioanalytical assays occurring prior to the achievement of the first quantifiable concentration will be assigned a concentration value of 0 to prevent overestimation of the initial AUC. Samples that are BLQ at all other time points will be treated as missing data in WinNonlin. The nominal time point for a key event or dosing interval ( $\tau$ ) may be used to permit direct calculation of AUC over specific time intervals. The appropriateness of this approach will be assessed by the PK scientist on a profile-by-profile basis.

Pharmacokinetic parameters such as  $AUC_{\tau}$ ,  $\lambda_z$  and  $t_{1/2}$  are dependent on an accurate estimation of the terminal elimination phase of drug. The appropriateness of calculating these parameters will be evaluated upon inspection of PK data on a profile-by-profile basis by the PK scientist.

#### 8.1.2. Pharmacokinetic Parameters

CCI

CCI

The analytes and parameters presented in Table 8-2 will be used to evaluate the PK objectives of the study. The PK parameters to be estimated in this study are listed and defined in the Pharmacokinetic Abbreviations section.

**Table 8-2. Pharmacokinetic Parameters for Each Analyte**

Analyte	Parameters
Filgotinib	AUC last , AUC tau , C tau , C max , T max , C last , T last , λ z , CL ss /F, V z /F, and t 1/2 , if appropriate
GS-829845	AUC last , AUC tau , C tau , C max , T max , C last , T last , λ z , and t 1/2 , if appropriate

### 8.1.3. Statistical Analysis Methods

Individual subject concentration data and individual subject PK parameters for filgotinib and GS-829845 will be listed and summarized using descriptive statistics by treatment. Summary statistics (number of subjects [n], mean, SD, coefficient of variation [%CV], median, minimum, maximum, Q1, and Q3) will be presented for both individual subject concentration data by time point and treatment; and individual subject PK parameters by treatment. Moreover, the geometric mean, 95% CI, and the mean and SD of the natural log-transformed values will be presented for individual subject PK parameter data.

Individual concentration data listings and summaries will include all subjects with concentration data. The sample size for each time point will be based on the number of subjects with nonmissing concentration data at that time point. The number of subjects with concentration BLQ will be presented for each time point. For summary statistics, BLQ values will be treated as 0 at predose and one-half of the lower limits of quantitation (LLOQ) for postdose time points.

Individual PK parameter data listings and summaries will include all subjects for whom PK parameter(s) can be derived. The sample size for each PK parameter will be based on the number of subjects with nonmissing data for that PK parameter.

The following tables may be provided for each analyte by treatment:

- Individual subject concentration data and summary statistics
- Individual subject plasma PK parameters and summary statistics.

CCI

Individual, mean, and median postdose concentration values that are ≤ LLOQ will not be displayed in the figures and remaining points connected.

The following listings will be provided:

- PK sampling details (and PK concentrations) by subject, including procedures, differences in scheduled and actual draw times, and sample age
- Individual data on determination of plasma half-life and corresponding regression correlation coefficient.

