3.2. Study Design

This is a randomized, double-blind, placebo- and active-controlled, Phase 3 study in adult male and female subjects with moderately to severely active RA who have limited or no prior exposure to MTX therapy. The study is designed to evaluate the efficacy, safety and tolerability of filgotinib as well as its effect on patient-reported outcomes, including work productivity, fatigue, and quality of life. In addition, PK will be assessed.

Adult male and female subjects with active RA will be screened to determine eligibility as per the inclusion and exclusion criteria (see Section 4.2 and 4.3, respectively). The Screening period will be up to 28 days. The screening window may be extended to up to 42 days prior to the Day 1 visit for subjects who require repeat collection of radiographs.

Written informed consent must be obtained before any study-related procedures take place. During the Screening period, following signing of the informed consent form (ICF), the subject's radiographs (hands, wrists, and feet) will be sent to central review for confirmation of joint erosion (see inclusion criterion 5; Section 4.2). Note that the subject's radiographs need to be sent to central review as soon as possible after completion and prior to Day 1 to allow for central reading and confirmation of one or more joint erosion in subjects that are seronegative.

Subjects will be randomized in a 2:1:1:2 ratio to filgotinib 200 mg plus MTX, filgotinib 100 mg plus MTX, filgotinib 200 mg alone, or MTX alone for up to 52 weeks in a double-blind fashion.

At Week 24, subjects who have not achieved a 20% improvement from Day 1 in both SJC and TJC will discontinue investigational therapy but will continue with study visits and assessments per protocol. All subjects who discontinue from investigational therapy are to receive standard of care treatment for their RA as determined by the investigator.

Responders at Week 24 will continue on the treatment regimens to which they were randomized through Week 52.

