6.8. Pharmacokinetics Assessments

For all subjects, blood samples for PK analysis will be collected at least 30 minutes post study drug dosing at Week 4, prior to study drug dose at Week 12 and Week 24, and at Week 52 or ET.

CCI

Plasma concentrations of filgotinib and GS-829845 will be analyzed.

Additional analyses (e.g., for MTX and its metabolites) may be performed.

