8.7. Pharmacokinetic Analysis

Plasma concentrations of filgotinib and its metabolite (GS-829845) will be listed and summarized for all subjects by treatment using descriptive statistics (eg, sample size, arithmetic mean, geometric mean, % coefficient of variation, standard deviation, median, minimum, and maximum).

CCI
[REDACTED]

Exposure-response analysis may be performed.

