#### **3.1.5. Pharmacokinetic Analysis Set**

The Pharmacokinetic (PK) Analysis Set includes all subjects in the Safety Analysis Set who have at least 1 nonmissing plasma concentration data for filgotinib and/or its metabolite GS-829845. This is the primary analysis set for general PK analyses.

CCI

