### 3.8.2. Analysis Visit Windows

Subject visits may not occur on protocol-specified days. Therefore, for the purpose of analysis, observations will be assigned to analysis windows.

In general, the baseline value will be the last nonmissing value on or prior to the first dose date of study drug, except for the mTSS baseline value. The mTSS baseline value will be derived based on the measurements collected on or prior to the first dose date of study drug + 14 days given the potential delay in scheduling an x-ray assessment..

For efficacy endpoints, vital signs, electrocardiogram (ECG), weight, lipid, and safety laboratory data, the analysis visit windows will be applied to data collected during the ‘on-treatment’ period. The ‘on-treatment’ period is defined as the last dose date of any study drug plus 7 days.

The analysis windows for on-treatment efficacy endpoints including joint count assessment, HAQ-DI (including subject’s pain assessment), subject’s global assessment (SGA), physician’s global assessment (PGA), serum CRP, CCI [REDACTED] and vital signs, weight, and safety laboratory data (lipid data excluded) are provided in [Table 3-1](#).

**Table 3-1. Analysis Visit Windows for On-treatment Joint Count Assessment, HAQ-DI, SGA, PGA, CRP, CCI [REDACTED] and Vital Signs, Weight, and Safety Laboratory Data (Lipid Data Excluded)**

Analysis Visit	Nominal Study Day	Lower Limit	Upper Limit
Baseline	1	(none)	1
Week 2	15	2	22
Week 4	29	23	43
Week 8	57	44	71
Week 12	85	72	99
Week 16	113	100	127
Week 20	141	128	155
Week 24	169	156	190
Week 30	211	191	232
Week 36	253	233	281
Week 44	309	282	337
Week 52	365	338	≥ 365

The analysis windows for on-treatment ECG data are provided in [Table 3-2](#).

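### Week 52 filgotinib concentration summaries carry no visible on-drug condition, so samples from subjects up to about 28 weeks off drug pull the filgotinib-arm means down

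*SAP*

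**What the plan says.** **Who is sampled.** Protocol 6.8 begins: "For all subjects, blood samples for PK analysis will be collected at least 30 minutes post study drug dosing at Week 4". It goes on to pre-dose samples at Weeks 12 and 24 and a sample at Week 52 or early termination. The footnotes to Protocol Appendix 2 allow the Week 52 sample at any time during the visit.

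**Who is still there.** Under Protocol 3.2, subjects without 20% improvement in both joint counts at Week 24 "will discontinue investigational therapy but will continue with study visits and assessments per protocol". Loss of response from Week 30, confirmed at two consecutive visits, is handled in the same way. Protocol 3.5.2 encourages subjects who stop for other reasons to keep attending.

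**Who is summarised.** Protocol 8.7 says that concentrations "will be listed and summarized for all subjects by treatment using descriptive statistics". SAP 8 repeats this without a condition. The PK Analysis Set (SAP 3.1.5) "includes all subjects in the Safety Analysis Set who have at least 1 nonmissing plasma concentration data", so one sample at any visit qualifies the subject. SAP 3.2 keeps subjects in their randomised arm unless their actual treatment differed throughout. SAP 8.1.3 states: "Individual concentration data listings and summaries will include all subjects with concentration data". It adds: "The sample size for each time point will be based on the number of subjects with nonmissing concentration data at that time point".

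**What is restricted.** SAP 3.8.2 defines an on-treatment period ending 7 days after the last dose of any study drug, and names its scope: "For efficacy endpoints, vital signs, electrocardiogram (ECG), weight, lipid, and safety laboratory data, the analysis visit windows will be applied". PK is not in that list, and Tables 3-1 to 3-6 give it no window. The further exclusions in SAP 6.1 concern efficacy data only.

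**How below-quantitation (BLQ) values are handled.** Protocol 8.3 sets BLQ to 0 only before the first dose and to half the LLOQ at all other times. SAP 3.7 uses 0 at predose time points and half the LOQ at postbaseline ones. SAP 8.1.3 says "BLQ values will be treated as 0 at predose and one-half of the lower limits of quantitation (LLOQ) for postdose time points".

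**The concern.** Followed as written, the plan averages samples from subjects who stopped filgotinib weeks or months earlier with samples from subjects still taking it, and reports the result as the arm's Week 52 concentration. The off-drug values say nothing about exposure on 200 mg or 100 mg. They are not missing, so they count in n, and the BLQ rule turns them into small positive numbers that enter the mean, the SD and the geometric mean.

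The SAP recognises the same problem for efficacy, vital signs, ECG, weight, lipids and laboratory data, and restricts those to on-treatment records. Concentrations depend on current dosing most directly, yet no such restriction is visible for them.

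At stake is the accuracy of a descriptive table. If an exposure-response analysis were run on these samples, there would also be a risk of reading a low concentration as the cause of non-response when non-response had caused the drug to be stopped.

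**Working it through.** The plan states no PK figure to reproduce. The check traces the rules and then sizes the effect under labelled assumptions.

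**1. Time off drug at the Week 52 sample.** For a subject stopped at Week 24: 52 − 24 = 28 weeks = 28 × 7 × 24 = 4,704 hours. The visible text gives no human half-life. At assumed half-lives of 5, 24 and 72 hours, that is 941, 196 and 65 half-lives. For loss of response confirmed at Weeks 36 and 44, the gap is 52 − 44 = 8 weeks = 1,344 hours, still 1,344 / 72 = 18.7 half-lives at the longest assumed value. These samples can be taken as BLQ.

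**2. Value assigned.** A Week 52 sample is postbaseline and comes after the first dose, so SAP 3.7 and Protocol 8.3 both give half the limit of quantitation. SAP 8.1.3, read alone, is less clear, because a sample from a subject no longer dosing is neither predose nor postdose.

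**3. Bound on the off-drug share f from the Week 24 rule.** ACR20 response (SAP 6.2.1) requires 20% improvement in both joint counts, so every ACR20 responder passes the rule. At the design rate of 78% (SAP 1.3), with complete data, at most 1 − 0.78 = 22% fail it: 0.22 × 400 = 88 subjects, or 0.22 × 200 = 44. The true share is lower to the extent that ACR20 non-responders fail only on the other five items. Later loss of response and other stops add to it; leaving the study reduces it.

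**4. Effect on the geometric mean.** Let G be the on-drug geometric mean, h half the LLOQ, and R = G/h. With a share f of samples set to h:

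log(mean) = (1 − f) log G + f log h, so reported/on-drug = (h/G)^f = R^(-f).

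| f (assumed) | R = 10 | R = 50 | R = 100 |
|---|---|---|---|
| 5% | 0.89 | 0.82 | 0.79 |
| 10% | 0.79 | 0.68 | 0.63 |
| 22% (bound in step 3) | 0.60 | 0.42 | 0.36 |

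**5. Effect on the arithmetic mean.** The ratio is (1 − f) + f/R, with R now the on-drug arithmetic mean over h. At f = 10% it is 0.90 + 0.10/10 = 0.91 for R = 10, and 0.90 + 0.10/100 = 0.901 for R = 100. The mean falls by roughly f.

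**6. After restriction to on-drug samples,** both ratios return to 1.

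**The case against.** The strongest reply is that this is a small matter in a partly redacted area. SAP 8.1.3 falls under the heading for intensive PK sampling, whose scope text is blacked out, so its all-subjects sentence may not govern the sparse Week 52 samples, and a condition inside redacted text cannot be excluded. The summaries are descriptive and no PK hypothesis is in the testing sequence. BLQ counts per time point and listings with draw times would help a careful reader see what happened. The Week 52 sample is drawn at an uncontrolled time after dosing, so its mean is not a formal exposure parameter.

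Most of this stands and limits the size of the point. It does not remove it, because Protocol 8.7, SAP 8 and SAP 3.1.5 are general text and show no on-drug condition. The display rules help only in part: under SAP 3.7 the first quartile is shown as BLQ only when more than 25% of values are BLQ, and the Week 24 rule alone gives at most about 22%. The means and geometric mean are reported in any case.

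Three stronger readings are tempting and are not supported:

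- *The arms would show a false exposure difference.* The sample-size text assumes 78% ACR20 in each filgotinib group, so the documents give no basis for different off-drug shares between them.
- *Early stoppers contaminate Weeks 12 and 24 at half-LLOQ in the same way.* Those samples are defined relative to a dose that an off-drug subject does not take, and SAP 3.7 could label them predose (0) or postbaseline (half-LOQ). The value is unsettled.
- *Even completers are off drug at Week 52.* Protocol 6 limits dosing to 52 weeks only as far as possible, and Protocol 3.3 tells subjects to hold that day's dose until instructed at a visit, which presumes continuing dosing.

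**Conclusion.** The point holds for the Week 52 concentration summaries in the filgotinib arms. The visible rules sample subjects who are long off drug, keep them in their arm, give their BLQ results a number, and do not exclude them. The bias is downward in both means. For the geometric mean it is a factor of 0.79 to 0.63 at an assumed f of 10% and R of 10 to 100. The documents supply neither f nor R; they support only the bound of about 22% on f from the Week 24 rule, at the design response rate and with complete data.

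No hypothesis test or efficacy conclusion changes. A reader might infer that the exposure-response results will be wrong. Protocol 8.7 says only that such an analysis may be done and names no dataset, and the Week 24 sample is scheduled at the same visit that triggers the stop, so that rule does not affect it. The supported statement is narrower: if the analysis is run, it should not use off-drug samples.

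**What to change.** In SAP 8, and in 8.1.3 if it is meant to cover the sparse samples:

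- Compute concentration summary statistics, and build any exposure-response dataset, only from samples drawn within a stated interval of the last filgotinib or placebo-to-match filgotinib dose. Do not use the last dose of any study drug, which includes weekly MTX.
- List the off-drug samples and report their number by visit and arm.
- Leave the PK Analysis Set in SAP 3.1.5 as it is. It selects subjects, and this rule selects samples.
- Reconcile the BLQ wording of Protocol 8.3 with SAP 3.7 and 8.1.3. A Week 12 or 24 pre-dose sample is both predose and postbaseline, and a value of 0 makes a geometric mean zero or undefined.

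The cost is a few lines of SAP text and one programming flag, using the per-drug last-dose dates that SAP 3.8.1 already derives. Those dates mark permanent withdrawal, which is the case at issue; excluding samples taken during temporary interruptions as well would need the dosing records. The one analytical downside is a smaller n at Week 52.

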## **9. BIOMARKER ANALYSIS**

A separate biomarker analysis plan (BAP) will document methods to analyze biomarker assessments.

## **11. SOFTWARE**

SAS® Software Version 9.X. SAS Institute Inc., Cary, NC, USA.

nQuery Advisor(R) Version X.0. Statistical Solutions, Cork, Ireland.

## 12. SAP REVISION

Revision Date (DD MMM YYYY)	Section	Summary of Revision	Reason for Revision

## **Appendix 1. Lists of RA Medications**

### **1) List of Oral Corticosteroid (WHO Preferred Terms)**

- BETAMETHASONE
- BETAMETHASONE DIPROPIONATE
- BETAMETHASONE SODIUM PHOSPHATE
- CORTISONE
- DEXAMETHASONE
- DEXAMETHASONE PALMITATE
- DEXAMETHASONE SODIUM PHOSPHATE
- HYDROCORTISONE
- MEPREDNISON
- METHYLPREDNISOLONE
- METHYLPREDNISOLONE ACETATE
- METHYLPREDNISOLONE SODIUM SUCCINATE
- MOMETASONE FUROATE
- PREDNISOLONE
- PREDNISOLONE FARNESYLATE
- PREDNISOLONE SODIUM SUCCINATE
- PREDNISON
- TRIAMCINOLONE

### **2) List of DMARDs and investigational bDMARDs (WHO Preferred Terms)**

- ABATACEPT
- ADALIMUMAB
- ANAKINRA

- BAMINERCEPT
- BELIMUMAB
- BIMEKIZUMAB
- CABIRALIZUMAB
- CERTOLIZUMAB
- CERTOLIZUMAB PEGOL
- CHLOROQUINE
- CHLOROQUINE PHOSPHATE
- CHLOROQUINE SULFATE
- CICLOSPORIN
- CLAZAKIZUMAB
- CORTISONE
- DENOSUMAB
- DEXAMETHASONE
- DEXAMETHASONE PALMITATE
- DEXAMETHASONE PHOSPHATE
- DEXAMETHASONE SODIUM PHOSPHATE
- EPRATUZUMAB
- ETANERCEPT
- GOLIMUMAB
- HYDROXYCHLOROQUINE
- HYDROXYCHLOROQUINE SULFATE
- INFLIXIMAB

- INTERLEUKIN INHIBITORS
- INTERLEUKIN-2
- LEFLUNOMIDE
- METHOTREXATE
- METHOTREXATE SODIUM
- OCRELIZUMAB
- PENICILLAMINE
- REMTOLUMAB
- RITUXIMAB
- SARILUMAB
- SECUKINUMAB
- SIRUKUMAB
- SULFASALAZINE
- TABALUMAB
- TILDRAKIZUMAB
- TOCILIZUMAB
- TREGALIZUMAB

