4.3. Exclusion Criteria

Subjects who meet *any* of the following exclusion criteria are not to be enrolled in this study.

1) Prior treatments for RA as follows:

- a) Alkylating agents, eg, chlorambucil or cyclophosphamide, at any time
- b) Previous treatment with any JAK inhibitor
- c) Previous therapy with csDMARDs other than MTX or hydroxychloroquine (eg, gold salts, cyclosporine, leflunomide, azathioprine, sulfasalazine or any other immunosuppressive).

NOTE: Subjects with prior exposure to csDMARD may be enrolled if the subject had limited exposure (less than 3 months of total exposure). Washout periods need to be satisfied per protocol (section 5.4).

- d) Use of any licensed or investigational biologic DMARDs (eg, B-cell depleting agents, tumor necrosis factor (TNF) alpha inhibitors, and/or interleukin (IL)-1, IL-6, IL-17, IL-12/23 inhibitors, including but not limited to abatacept, anakinra, certolizumab pegol, etanercept, golimumab, infliximab, rituximab, secukinumab, ustekinumab or tocilizumab
- 2) Known hypersensitivity or allergy to study drug, its metabolites, or formulation excipients.
 - 3) Known hypersensitivity or allergy to the MTX, its metabolites, or formulation excipients.
 - 4) Oral steroids at a dose >10 mg/day of prednisone (or equivalent) or a prescription for oral steroids which has changed within 4 weeks of Day 1.
 - 5) Receipt of an intra-articular or other injectable corticosteroid within 4 weeks prior to Day 1.
 - 6) Use of nonsteroidal anti-inflammatory drugs (NSAIDs) which have not been at a stable dose (defined as no change in prescription) for at least 2 weeks prior to Day 1. NOTE: subjects are permitted to take acetylsalicylic acid at a dose of ≤ 325 mg daily for cardiac prophylaxis, or occasional NSAIDs for non-RA indications (eg, headache).
 - 7) Administration of a live/attenuated vaccine within 30 days from Day 1, or planned during the study.
 - 8) Participation in any clinical study of an investigational drug/device within 4 weeks or 5 half-lives prior to Screening, whichever is longer. Exposure to investigational biologics are excluded as outlined in 1d.
 - 9) Have undergone surgical treatments for RA, including synovectomy or arthroplasty in >4 joints

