### 5.2. Baseline Disease Characteristics

Baseline disease characteristics include:

- Duration of RA from diagnosis (years)

Calculated as ((first dose date) – (date of initial diagnosis) + 1 day) / 365.25. If the date of initial diagnosis is incomplete, then the following rules will be applied:

— missing day: use the first of the month.

— missing month: use January.

- Presence of RF (Yes/No)
- Presence of anti-CCP Ab (Yes/No)

- Presence of RF and anti-CCP Ab (Yes/No)
- Concurrent oral corticosteroid use on the first dosing date (Yes/No): n(%)
  - Oral corticosteroids dose, mg/day, expressed as prednisone-equivalent dose, mean (SD)
- Concurrent anti-malarials use on the first dosing date (Yes/No): n(%)
- DMARD and investigational bDMARD naïve
- Swollen joint count based on 66 joints (SJC66)
- Tender joint count based on 68 joints (TJC68)
- Swollen joint count based on 28 joints (SJC28)
- Tender joint count based on 28 joints (TJC28)
- HAQ-DI total score
- DAS28(CRP)
- SF-36 PCS score
- SF-36 MCS score
- FACIT-Fatigue
- Subject's global assessment of disease activity (SGA, by visual analog scale [VAS] in mm)
- Physician's global assessment (PGA, by VAS in mm)
- Subject's pain assessment (by VAS in mm)
- Simplified Disease Activity Index (SDAI)
- Clinical Disease Activity Index (CDAI)
- hsCRP (mg/L)
- mTSS
  - Erosion score
  - Joint space narrowing score

These baseline characteristics will be summarized by treatment group and overall using descriptive statistics for continuous variables and using number and percentage of subjects for categorical variables. The summary of baseline characteristics will be provided for the Safety Analysis Set.

A by-subject listing of other baseline characteristics will be provided by subject ID number in ascending order.

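### The SAP's DMARD term list contains five corticosteroid terms and omits azathioprine and gold salts, so it can misclassify subjects in either direction if it derives the DMARD-naive baseline row.

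*SAP*

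**What the plan says.** SAP Appendix 1 holds two lists of WHO preferred terms.

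- List 1 is headed "List of Oral Corticosteroid (WHO Preferred Terms" and covers steroids.
- List 2 is headed "List of DMARDs and investigational bDMARDs (WHO Preferred Terms". It contains cortisone, "DEXAMETHASONE", "DEXAMETHASONE PALMITATE", "DEXAMETHASONE PHOSPHATE" and "DEXAMETHASONE SODIUM PHOSPHATE".
- SAP Appendix 5, the prednisone-equivalence table, includes all five of these as corticosteroids.

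SAP 5.2 lists "DMARD and investigational bDMARD naïve" among the baseline disease characteristics, summarised by treatment group and overall for the Safety Analysis Set. It gives no derivation rule and no reference to Appendix 1. The one pointer to Appendix 1 in the SAP body is in section 3.4, and it concerns oral corticosteroids.

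Protocol 4.3, criterion 1c, gives these examples of csDMARDs: "gold salts, cyclosporine, leflunomide, azathioprine, sulfasalazine or any other immunosuppressive". The note beneath it lets subjects with less than 3 months of total csDMARD exposure enrol, subject to washout.

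**The concern.** A term list is applied mechanically: a subject with a coded prior medication on the list is counted as exposed. List 2 is inconsistent with its heading in two ways.

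- **Terms that do not belong.** Someone with recorded dexamethasone or cortisone and no DMARD would be counted as DMARD-experienced.
- **Terms that are missing.** Someone whose only DMARD was azathioprine or a gold salt would be counted as naive.

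The steroid terms do not look like a deliberate widening of the definition. Prednisone, prednisolone and methylprednisolone are rightly absent from list 2, and SAP 5.2 already reports oral corticosteroid use as its own characteristic. No consistent definition of a DMARD takes in dexamethasone but leaves out both prednisone and azathioprine.

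At stake is one line of the baseline table, in a trial whose population is defined partly by limited prior treatment.

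**Working it through.** The documents state no DMARD-naive percentage, so there is no plan figure to reproduce. The check compares the lists term by term.

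**1. List 2 against the SAP's own steroid lists**

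| Term in list 2 | In list 1 (oral corticosteroids) | In Appendix 5 (steroid table) |
|---|---|---|
| Cortisone | yes | yes |
| Dexamethasone | yes | yes |
| Dexamethasone palmitate | yes | yes |
| Dexamethasone phosphate | no | yes |
| Dexamethasone sodium phosphate | yes | yes |

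List 2 has 43 terms. Five are corticosteroids by Appendix 5, and four of those are also in list 1.

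**2. List 2 against the agents named in Protocol 4.3**

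- Criterion 1c names five csDMARDs as examples. Ciclosporin, leflunomide and sulfasalazine are in list 2; azathioprine and gold salts are not.
- Criterion 1d names ten biologics. Nine are in list 2; ustekinumab is not. Prior biologic use is an exclusion, so this gap matters only for protocol violators.

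**3. Can eligible subjects be affected?**

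- Short csDMARD exposure is allowed, so azathioprine or gold users can be enrolled without a violation.
- Protocol 5.4 allows stable oral prednisone up to 10 mg/day or equivalent, which can include dexamethasone or cortisone.
- Protocol 5.4 records all prior RA medication without a time limit, but non-RA medication only if used within 30 days of consent.

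**4. Effect on the percentage**

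Let F1 be the number of truly naive subjects with one of the five steroid terms on record. Let F2 be the number whose only DMARD was azathioprine or gold. Then

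net shift in the naive percentage = 100 × (F2 − F1) / N.

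One misclassified subject moves it by:

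- all subjects: 100/1200 = 0.08 points
- an arm of 400: 100/400 = 0.25 points
- an arm of 200: 100/200 = 0.50 points

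The documents give neither F1 nor F2. Purely as an illustration, assume F1 is 0–5% and F2 is 0–2% of subjects. These ranges are assumptions with no basis in the documents. The extremes are 0 − 5.0 = −5.0 points and 2.0 − 0 = +2.0 points. The shift is zero if neither group occurs or if the two are equal.

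**The case against.** The list contents are not in dispute, but the consequence can be pressed too far.

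- **The link is inferred.** SAP 5.2 does not say that list 2 derives the row. This stands. The near-identical wording makes the link likely. If list 2 is not the source, the row has no definition and the list has no stated purpose, so the SAP still needs a correction.
- **The steroid error is narrower than it looks.** A reader might infer that any past dexamethasone course turns a subject into a DMARD-experienced one. The documents do not support that: a course for a non-RA reason is recorded only within 30 days of consent. The exposed group is mainly subjects treated for RA, plus recent users. Criterion 5 of Protocol 4.3 also excludes anyone given an injectable corticosteroid in the 4 weeks before Day 1.
- **The information appears elsewhere.** SAP 7.4 and 7.4.1 summarise prior medications by preferred name and treatment group, with RA-specific and general medications separate. Azathioprine, gold or dexamethasone would appear there under its own name. A reader might infer that prior DMARD exposure as a whole, or MTX-naivety, would be misreported. That does not follow: MTX-naivety is set by inclusion criterion 5, and only one derived yes/no row is at risk.

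These points limit the consequence. They do not make the list correct.

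**Conclusion.** List 2 does not match its heading and should be corrected. If it derives the row in SAP 5.2, as the wording suggests, it can misclassify subjects in both directions.

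A reader might go further and infer that the reported percentage is bound to be wrong, or wrong by a particular amount. The documents do not support that. An error needs at least one subject whose only listed drug is one of the five steroids, or whose only DMARD is an omitted one, and no prior-medication counts are given. The two errors also oppose each other. Cancellation in the total would not make the individual classifications right, however, and the table is also presented by treatment group.

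The importance is low. The row is descriptive. It is not a stratification factor, a model covariate, a subgroup listed in SAP 3.4, a per-protocol criterion in SAP 3.1.3 or part of any endpoint. No efficacy analysis changes.

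**What to change.** 1. In SAP Appendix 1, list 2, delete cortisone, dexamethasone, dexamethasone palmitate, dexamethasone phosphate and dexamethasone sodium phosphate.
2. Add azathioprine and the gold salt preferred terms. Add ustekinumab for completeness; it can matter only for protocol violators.
3. In SAP 5.2, state that list 2 defines the row, give the look-back period, and say whether permitted prior MTX or antimalarial use counts as exposure. Both drug groups are in list 2, so the meaning of naive depends on the answer.

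The cost is an edit to one list and a short definition. SAP section 1 places SAP finalisation before the Week 24 database is finalised, so the change fits there. If the SAP is already final, the same section provides for documenting it in the clinical study report.
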